in comparison to placebo along with corresponding two-sided 95% confidence intervals (CIs) and p-values will also be presented.

Additionally, change from baseline in SARS-CoV-2 viral load at Day 3, 7, 14 and 28 will be compared using a mixed model repeated measures (MMRM). The model will include treatment group, visit, treatment-by-visit interaction, age and stratification factors (sex, race and ethnicity, and number of risk factors) as fixed effects, baseline viral load as a covariate, and subject as a random effect. If the unstructured covariance matrix fails to converge, the heterogeneous Toeplitz covariance structure, followed by the heterogeneous autoregressive covariance structure, will be used. If systematic pattern is found in the residual of predicted values, a transformation of the baseline viral load will be employed to improve the performance of the model. Comparisons of GT0918 to placebo for change from baseline in viral load and the corresponding two-sided 95% CIs along with p-values will be calculated and plotted based on the MMRM model at each visit.

Sustained 100% SARS CoV-2 Viral Reduction

SARS-CoV-2 viral reduction (%) is calculated as

$$(\text{viral load after baseline} - \text{viral load at baseline}) / (\text{viral load at baseline}) * 100\%.$$

If the value of SARS-CoV-2 viral reduction is greater than or equal to 100 the result of 100% SARS CoV-2 viral reduction will be set as "Yes". Otherwise, a negative result of "No" will be obtained.

Sustained 100% SARS CoV-2 viral reduction (Yes/No) is defined when at least two consecutive negative ("No") tests (≥ 24 hours apart) are obtained. The date of sustained 100% SARS CoV-2 viral reduction is defined as the earlier date of the consecutive negative tests.

The proportion of subjects that achieve sustained 100% SARS CoV-2 viral reduction at Days 3, 7, 14, and 28 will be summarized by treatment in frequency tables, plotted and listed. Generalized estimating equation (GEE) model will be used to model the proportions of achieving SARS-CoV-2 clearance at different visits. The model will consider treatment group, visit, treatment-by-visit interaction, age and stratification factors (sex, race and ethnicity, and number of risk factors) as fixed effects, and subject as a random effect. Comparisons of GT0918 to placebo for odds ratios (ORs), corresponding 95% CIs and p-values will be calculated at each visit.

Time to Sustained 100% SARS CoV-2 Viral Reduction

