Note: * Nine individual questions from COVID-19-Related Symptom Questionnaire are included here: questions 1 through 9.

The proportion of subjects with all symptom resolution will be performed at Days 3, 7, 14, and 28 by treatment in frequency tables and listed using mITT set. Generalized estimating equation (GEE) model will be fitted with the response of symptom resolution mapped to categories of Yes or No and with treatment, age, stratification factors (sex, race and ethnicity, and number of risk factors), time

effect and time*treatment interaction terms included in the model as covariates. Odds ratios with 95% confidence intervals and p-values will be present.

Total symptom score (seven individual questions from COVID-19-Related Symptom Questionnaire included here are questions 3, 4, 5, 6, 7, 8 and 9) and change from baseline in total symptom score to Days 3, 7, 11, 14 and 28 will be summarized by treatment group. Change from baseline will be compared using mixed model repeated measures (MMRM) with the fixed effects of baseline total symptom score, age and stratification factors (sex, race and ethnicity, and number of risk factors) and the random effect of subjects and with time effect and time*treatment interaction terms included in the model. Change from baseline in total symptom score will also be graphically displayed.

Additionally, total symptom score will be calculated differently to include nine individual questions (1 through 9) and related outputs will be noted as sensitivity analysis.

A summary of overall COVID-19 related symptoms, including overall symptoms severity, overall general physical health and returned to usual physical health, at Days 3, 7, 11, 14 and 28 will be provided in frequency table and listed.

Additionally, the proportion of subjects with at least 2 points decrease in symptom score (total of ratings) from baseline to Days 3, 7, 14 and 28 will be summarized and listed as well. Generalized estimating equation (GEE) model will be fitted with the response of at least 2 points decrease mapped to categories of Yes or No and with treatment, age, stratification factors (sex, race and ethnicity, and number of risk factors), time effect and time*treatment interaction terms included in the model as covariates. Odds ratios with 95% confidence intervals and p-values will be present.

Time to All Symptom Resolution

Time to all symptom resolution (in days) is defined as:

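### Both MMRMs of change from baseline fit one baseline slope for all visits; a baseline-by-visit term, with a stated covariance for the symptom model, would avoid an avoidable loss of precision

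*SAP*

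**What the plan says.** SAP 4.10.3 specifies two repeated-measures models of change from baseline.

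- **Viral load (log10), Days 3, 7, 14 and 28.** "The model will include treatment group, visit, treatment-by-visit interaction, age and stratification factors", with "baseline viral load as a covariate, and subject as a random effect". The covariance is unstructured, with heterogeneous Toeplitz and then heterogeneous autoregressive as fallbacks. If residuals show a pattern, "a transformation of the baseline viral load will be employed to improve the performance of the model". Separately, there are two-sample t-tests at each visit and an ANCOVA at Day 3 with baseline viral load as covariate.
- **Total symptom score (questions 3 to 9).** The summary covers "change from baseline in total symptom score to Days 3, 7, 11, 14 and 28". For the model: "Change from baseline will be compared using mixed model repeated measures (MMRM) with the fixed effects of baseline total symptom score", with age and the stratification factors as further fixed effects, plus "the random effect of subjects", "with time effect and time*treatment interaction terms included in the model". No residual covariance structure is named.

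In both models treatment is crossed with visit and baseline is not. Neither the protocol nor the SAP gives a mean, SD or correlation for either outcome.

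**The concern.** The outcome is change, and both scales have a floor. The symptom score cannot go below 0 (seven items scored 0 to 3, so 0 to 21). Viral load has a limit of quantification of 59.9 copies/mL, or 1.78 on the log10 scale. On Day 3 a subject's value still tracks baseline, so the slope of change on baseline is well above -1. Once a subject reaches the floor, change equals a constant minus baseline, and the slope is -1. The visit slopes are therefore expected to differ.

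A slope of -1 on change is the same as no baseline adjustment of the post-baseline value. If the common slope is pulled towards -1, early contrasts lose adjustment. If it settles in the middle, the last visit is badly fitted instead. Transforming baseline viral load still leaves one slope for all visits.

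At stake is the precision of the by-visit treatment contrasts, and their exposure to chance baseline imbalance.

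**Working it through.** **Plan figure.** The documents state no precision or power for either MMRM. The 668 subjects and about 90% power (SAP 4.12) concern the primary endpoint only.

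**Formulas** (complete data, baseline SD set to 1). At visit t let s be the SD of the post-baseline value and r its correlation with baseline.

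- Slope of change on baseline: b = r·s - 1. Residual variance: v = s²(1 - r²).
- Common slope under an unstructured covariance S: β = (1'S⁻¹b)/(1'S⁻¹1). Under a random intercept (compound symmetry), β is the plain mean of the visit slopes.
- Contrast variance, common slope relative to visit-specific slope: [v + (β - b)²]/v.
- Share of the baseline adjustment lost: (β - b)²/(r²s²). This equals 1 when β = -1.

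**Assumed base case** (viral-load visits):

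| Day | s | r | b | v |
|---|---|---|---|---|
| 3 | 1.0 | 0.5 | -0.50 | 0.750 |
| 7 | 0.8 | 0.4 | -0.68 | 0.538 |
| 14 | 0.5 | 0.2 | -0.90 | 0.240 |
| 28 | 0.3 | 0.1 | -0.97 | 0.089 |

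*Unstructured, autoregressive residual correlation 0.3 to 0.7.* β is -0.91 to -0.97, because the low-variance late visits dominate. At β = -0.95 the Day 3 ratio is (0.75 + 0.45²)/0.75 = 1.27; over the range it is 1.23 to 1.30. The share of Day 3 adjustment lost is 68% to 89%. For a hypothetical contrast with 90% power, (1.96 + 1.28)/√1.27 - 1.96 = 0.92, which is 82% power (range 81% to 83%; Day 7: 85% to 87%).

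*Unstructured, slower resolution (s = 1, 1, 0.8, 0.6).* The Day 3 ratio is 1.11 to 1.15, the share lost 33% to 46%, and power 86% to 87%.

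*Random intercept, base case.* β = -(0.50 + 0.68 + 0.90 + 0.97)/4 = -0.76.

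- Day 3: (0.75 + 0.26²)/0.75 = 1.09.
- Day 7: 1.01.
- Day 28: (0.0891 + 0.2075²)/0.0891 = 1.48, which takes 90% power to 76%.

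*Equal slopes at all visits.* The ratio is 1.00, so there is no loss.

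**Check with floors built in.** Simulation with N = 668, bounded 0 to 21 scores and floored log10 loads. Assumed baseline SDs were 4 (symptoms) and 2 log10 (viral load); correlations with baseline were 0.4 to 0.65 at Day 3, falling to 0.15 to 0.35 at Day 28.

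| Setting | Day 3 ratio | Day 3 share lost | Day 28 ratio |
|---|---|---|---|
| Unstructured, Day 28 near floor (about 9% still symptomatic, or 13% above LoQ) | 1.60 (1.14 with weak baseline correlation) | 82% to 85% | about 1.0 (symptom runs) |
| Unstructured, slower (27% to 55% symptomatic, or 44% above LoQ) | 1.12 to 1.32 | 16% to 49% | not the main loss |
| Random intercept | 1.03 to 1.22 | 15% to 30% | up to 2.3 to 2.6 |

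In the five-visit symptom run near the floor, the visit slopes were -0.37, -0.58, -0.71, -0.82 and -0.97. Their mean is -3.45/5 = -0.69, which is the random-intercept slope. The unstructured fit gave -0.95. The lower end of the random-intercept Day 28 range, about 1.1, comes from slower resolution: the closed form with s = 1, 1, 0.8, 0.6 gives 1.14.

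**The case against.** A reader might infer that the early contrasts lose most of their baseline adjustment because Day 28 change is nearly minus baseline. The documents do not support that as a general statement.

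- No document gives the Day 28 distribution. The only related figures are in Protocol 1.2.3.2 (men in the earlier COVID-19 study). There, control-arm RT-PCR positivity was 93.8% on Day 7, 56.2% on Day 14 and 43.8% on Day 28, against 10.0% on active treatment at Day 28. Values do fall, but for viral load the control arm is closer to the slower case, where well under half to about half of the Day 3 adjustment is lost. Those figures also show the arms apart as late as Day 28, so early visits are not the only ones that matter.
- The pull towards -1 needs a covariance that lets late visits have smaller variance. The SAP names one for viral load but not for symptoms. A literal random intercept leaves Day 3 and Day 7 of the symptom score little affected.
- Day 3 viral load has its own ANCOVA with its own baseline slope.
- Under randomization this is neither bias nor a Type I error problem. Both analyses are secondary, and the trial is not powered on them.

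All of this stands and limits the size of the point. It does not remove it. Viral load at Day 7 has only unadjusted t-tests besides the MMRM. For the symptom score, the GEE for a decrease of at least 2 points adjusts for age and the stratification factors but not for baseline score. Where slopes differ, a single slope costs precision at some visit under either covariance reading.

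**Conclusion.** The point holds as an avoidable loss of precision in two secondary analyses. Neither MMRM lets the baseline slope vary by visit, although it is expected to.

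- **Unstructured covariance (viral load as written):** Day 3 contrast variance is about 1.1 to 1.6 times larger. Most of the adjustment is lost only if Day 28 values lie near the floor.
- **Random-intercept reading of the symptom model:** the Day 3 excess is about 3% to 22%, and Day 28 can be the worst visit (ratio about 1.1 to 2.6).

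These ranges assume complete data and the SDs and correlations listed above; none comes from the documents. A stronger Day 3 correlation would go beyond them: at 0.7, with the base-case SDs and an unstructured covariance, the Day 3 ratio is about 1.7. The primary analysis and the Day 3 viral-load ANCOVA are untouched.

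**What to change.** In SAP 4.10.3:

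1. Add baseline log10 viral load × visit to the viral-load MMRM and baseline total symptom score × visit to the symptom MMRM, keeping the other fixed effects as written.
2. State the symptom MMRM's covariance: the same unstructured matrix, with the same fallback sequence, as for viral load. Without this, the reader cannot tell which visits the model serves well.

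The cost is 3 degrees of freedom for viral load (four visits) and 4 for symptoms (five visits) among about 668 subjects. It needs SAP wording only and no new data. If the slopes turn out equal, almost nothing is lost.

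### The symptom-score MMRM names only a random subject effect, which read literally is compound symmetry; the viral-load MMRM adds a redundant subject effect to an unstructured matrix

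*SAP*

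**What the plan says.** SAP section 4.10.3 contains two mixed models for repeated measures.

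- **Total symptom score** (under Proportion of Symptom Resolution). The score sums questionnaire items 3 to 9. The text says that "change from baseline in total symptom score to Days 3, 7, 11, 14 and 28 will be summarized by treatment group". Change is then compared by an MMRM. Its listed fixed effects are the baseline score, age and the stratification factors, and the rest of the model is given as "and the random effect of subjects and with time effect and time*treatment interaction terms included in the model". That is the whole covariance specification. Treatment enters only through its interaction with time, and no by-visit interval or p-value is named for this model.
- **Viral load.** Here "change from baseline in SARS-CoV-2 viral load at Day 3, 7, 14 and 28 will be compared using a mixed model repeated measures (MMRM"). Fixed effects in that model include treatment, visit and their interaction, with "baseline viral load as a covariate, and subject as a random effect". On covariance structure, the SAP then says: "If the unstructured covariance matrix fails to converge, the heterogeneous Toeplitz covariance structure, followed by the heterogeneous autoregressive covariance structure, will be used". By-visit output is explicit: "two-sided 95% CIs along with p-values will be calculated and plotted based on the MMRM model at each visit".

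The protocol does not fill the gap. Its section 10.5.2 gives no model for change in symptom score, and section 10.5.2.9 asks only for a linear mixed-effect model for viral load. Neither document gives an SD for either outcome at any visit.

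**The concern.** The SAP states a covariance structure, with two fallbacks, for one MMRM and none for the other. A programmer who follows the symptom-score text as it stands would fit a random intercept with independent residuals. That forces one variance on all visits. Where the true spread is above the average, the standard error is too small; where it is below, too large. Early visits are where an effect on symptoms would be looked for, and late visits are where most subjects have reached zero.

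In the viral-load model the problem is excess, not omission. The unstructured matrix already holds everything that a random subject effect could contribute. If the software fails to converge for that reason, the SAP's own rule moves the analysis to a second-line structure because of the wording and not because of the data.

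**Working it through.** **Inputs.** From the documents: seven items scored 0 to 3 (SAP 4.10.3 and 6.4), so the score runs from 0 to 7 × 3 = 21; symptom-score visits at Days 3, 7, 11, 14 and 28; viral-load visits at Days 3, 7, 14 and 28; about 668 subjects randomized 1:1 (SAP 3.1), so 334 per arm. Visit SDs are not given and are assumed below.

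**The plan's own figures.** There is none for either MMRM. The sample size reproduces: 334 per arm, 97% against 91%, one-sided 0.025 and an interim at half the information give 90.3% (pooled variance) to 90.8% (unpooled) power. Nothing here touches it.

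**Step 1: symptom score, literal model.** With complete data, a random intercept plus independent residuals estimates the total variance as the mean of the visit variances. So, at visit t,

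model SE / true SE = √(mean of visit variances) / SD_t

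and two-sided type I error = 2Φ(−1.96 × ratio).

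Example with SDs 3.5, 3.0, 2.5, 2.0, 1.5: mean variance = (12.25 + 9 + 6.25 + 4 + 2.25)/5 = 6.75, and its root is 2.598. The Day 3 ratio is 2.598/3.5 = 0.74, giving an error of 14.6%. The Day 28 ratio is 2.598/1.5 = 1.73, giving 0.1%.

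| Assumed SD, Days 3/7/11/14/28 | Ratio, Day 3 | Ratio, Day 28 | Type I, Day 3 | Day 7 | Day 28 |
|---|---|---|---|---|---|
| 3 at every visit | 1.00 | 1.00 | 5.0% | 5.0% | 5.0% |
| 3.2, 3.0, 2.8, 2.6, 2.2 | 0.87 | 1.26 | 8.8% | 6.9% | 1.3% |
| 3.5, 3.0, 2.5, 2.0, 1.5 | 0.74 | 1.73 | 14.6% | 9.0% | 0.1% |
| 4, 3, 2, 1.5, 1 | 0.63 | 2.54 | 21.3% | 9.7% | <0.1% |

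**Step 2: fitted models.** The third row was simulated with autoregressive correlation 0.7, 0 to 12% dropout and a random-intercept fit (150 null trials). The mean model SE was 0.204 to 0.213 at every visit. The empirical SD of the estimate ran from 0.304 (Day 3) to 0.133 (Day 28). Rejection was 19% at Day 3 (29 of 150, Monte Carlo SE about 3 points) and 0 of 150 at Day 28.

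**Step 3: assumed recovery curves.** Null trials of 668 subjects with a 0 to 21 score, tested with the pooled variance:

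| Assumption | Day 3 | Day 7 | Day 28 |
|---|---|---|---|
| Lognormal recovery, median 6 / 8 / 10 days, baseline slope free at each visit | 15.0 / 12.0 / 7.7% | 10.1 / 9.5 / 8.5% | 0–0.1% |
| Two other curve shapes, same medians | 4.3–13.1% (common slope), 3.6–10.3% (visit slopes) | about 7–13% | 0–1.1% |
| Nine further scenarios, one common baseline slope as in the SAP | about 6–27% | 7–11% | 0–0.6% |

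Visit-specific variances gave 4.2 to 5.8% in the first set and about 4 to 6% in the third. In most of the second set the residual SD was higher at Day 7 than at Day 3, so spread need not fall steadily.

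**Step 4: viral load.** An unstructured matrix U over four visits has 4 × 5/2 = 10 parameters. A random intercept makes the marginal covariance V = U + τ²J, where J is all ones. Replacing U by U − cJ and τ² by τ² + c leaves V unchanged, so τ² is not identifiable: 11 parameters, rank 10. V itself, the treatment contrasts and their standard errors remain estimable. Under the fallbacks the subject effect is identifiable: heterogeneous Toeplitz has 7 + 1 = 8 parameters (rank 8) and heterogeneous AR(1) has 5 + 1 = 6 (rank 6).

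**The case against.** The strongest reply is that MMRM conventionally implies an unstructured matrix, and that this SAP uses the random-effect phrase loosely. It lists subject as a random effect in its GEE models too, where it can only mark the cluster. On that view the symptom-score text is silent on the residual structure and does not prescribe compound symmetry. This is fair: the literal reading is one reading. But the same section names a structure for viral load and none here, and the one term it does name yields a definite model if programmed as written.

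A reader might infer more than the documents support:

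- **That the symptom-score standard errors are wrong.** They are correct under equal variances and exchangeable correlation, and no visit SDs are given.
- **That a particular Day 3 error rate applies.** Day 3 depends heavily on the assumed curve and was near nominal with slow recovery. Day 7 inflation and Day 28 conservatism were the stable findings.
- **That the viral-load model cannot be estimated.** Only the separate subject variance cannot, and no actual convergence failure has been shown.
- **That the missing treatment main effect is an error.** With categorical time, time plus time-by-treatment spans the same by-visit contrasts.
- **That by-visit p-values are a stated output for the symptom score.** They are explicit only for viral load; for symptoms they are inferred from the interaction term.

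The stakes are also limited. SAP 4.10.1.2 adjusts only for the interim, so these p-values are nominal. Viral load also has t-tests and a Day 3 ANCOVA; symptoms also have GEE and time-to-event analyses.

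**Conclusion.** The point holds in limited form. The symptom-score MMRM leaves its residual structure unstated, and its literal reading misstates by-visit standard errors unless variances are equal across visits. Equal variances are unlikely for a score bounded at 0 in recovering subjects. The size rests on assumed recovery curves: roughly 6 to 15% two-sided type I error at early visits in typical cases, higher with fast recovery and near 5% with slow, and about 1% or less at Day 28.

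The viral-load redundancy follows from algebra and needs no assumption about the data. Its consequence, an unnecessary move to the fallback, is a risk and not a certainty. The correction should be made, but it bears on two secondary analyses only.

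**What to change.** **Symptom score.** Replace the random subject effect with an unstructured within-subject covariance over categorical visits. List the fixed effects as treatment, visit, treatment-by-visit, baseline score, age and the stratification factors. Apply the fallback order already stated for viral load.

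**Viral load.** In "baseline viral load as a covariate, and subject as a random effect", delete everything after the comma and leave the rest of the model as it is.

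**Cost.** Two sentences of SAP text and no new data. The symptom-score model then carries 5 × 6/2 = 15 covariance parameters, which about 668 subjects support.
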